## 12.5 Reporting of Adverse Events

It is the responsibility of the Investigator to adhere to the adverse event reporting requirements as stated within the protocol and to their IRB reporting requirements. In case of an emergency or to immediately report a subject death and/or SADE, contact a study representative (refer to the study contact list provided in the study site's study documents binder/investigator site file or refer to the Sponsor contact information provided on the title page).

### 12.5.1 Adverse Event and Device Deficiency Classification

All AEs and DDs will be reviewed by a Medtronic representative. AEs will be classified according to the definitions provided.

Upon receipt of AE at Medtronic, a Medtronic representative will review the AE/DD for completeness and accuracy and when necessary will request clarification and/or additional information from the Investigator. Medtronic will utilize MedDRA for Regulatory Activities, to assign a MedDRA term for each AE based on the information provided by the investigator.

Regulatory reporting of AEs and DDs will be completed according to local regulatory requirements. Refer to [Table 12-3](#) for a list of required investigator and Medtronic reporting requirements and timeframes. It is the responsibility of both to abide by any additional AE reporting requirements stipulated by the IRB responsible for oversight of the study. AEs will be classified according to the standard definitions as outlined below:

**Table 12-2: Adverse Event Classification Responsibilities**

What is classified	Who Classifies	Classification Parameters
Relatedness	
 
• Investigator
 
• Sponsor
 
	
 
• Device related
 
• Therapy related
 
• Procedure related
 
 
Only events that are classified as possible, probable or causal are considered to be related.

Seriousness	
 
• Investigator
 
• Sponsor
 
	SAE
Diagnosis	Investigator	Based on presenting signs and symptoms and other supporting data
	Sponsor	MedDRA term assigned based on the data provided by Investigator

### **12.5.2 Adverse Event and Device Deficiency Reporting Requirements**

Regulatory reporting of AEs and DDs will be recorded and reported according to local regulatory requirements. It is the responsibility of the Investigator and the sponsor to abide by the AE reporting requirements stipulated by local law and the study site's IRB.

**Table 12-3: Reporting Requirements**

ADEs	
Investigator shall submit to:	
Medtronic	Submit in a timely manner (within 3 weeks) after the investigator first learns of the effect.
IRB	Submit to IRB per local reporting requirement.
Sponsor shall submit to:	
IRB	Submit to IRB per local reporting requirement.
SADEs	
Investigator shall submit to:	
Medtronic	Submit in a timely manner (within 3 weeks) after the investigator learns of the event or of new information in relation to an already reported event.
IRB	Submit to IRB per local reporting requirement.
Sponsor shall submit to:	
IRB	Submit to IRB per local reporting requirement.
Investigators	Submit per local reporting requirement.
All Other Reportable AEs	
Investigator shall submit to:	
Medtronic	Submit in a timely manner (within 5 weeks) after the investigator first learns of the event.
IRB	Submit to IRB per local reporting requirement.
Device Deficiencies	
Investigator shall submit to:	
Medtronic	Submit in a timely manner (within 5 weeks) after the investigator first learns of the deficiency.
IRB	Submit to IRB per local reporting requirement.

## 12.6 Subject Death

The investigator must notify Medtronic immediately and the IRB, as required, after learning of a subject's death, regardless of whether or not the death is related to the device system, therapy or procedure. In case of death that is device-related, therapy-related, or procedure-related, there should be one AE with the outcome of death. All other deaths will be recorded on a study exit CRF.

In the event of a subject's death, it is recommended that the implanted system be explanted and returned to Medtronic for analysis whenever possible per local process. Local laws and procedures must be followed where applicable. If any system component is returned to Medtronic, internal return

product reporting systems may be used to gather additional information about the returned device/component.

A copy of the death certificate, if available and allowed by state/local law, should be sent to the Medtronic clinical study team. When a death occurs in a hospital, a copy of the death summary report and all relevant hospital records, if available should be sent to the Medtronic clinical study team. If an autopsy is conducted, a copy of the autopsy report should also be sent to the Medtronic clinical study team if available and allowed by state/local law. When the death occurs at a remote study site, it is the investigative study site's responsibility to attempt retrieval of information about the death. Additionally, device disposition information should be updated.

In summary, the following data will be collected:

- Date of death
- Detailed description of death
- Cause of death
- Relatedness to system and/or procedure
- Device interrogation information/reports and Save-to-Media information/reports (if available)
- Device disposition information
- Death summary/hospital records (if available and allowed by state/local law)
- Autopsy report (if available and allowed by state/local law)
- Death certificate (if available and allowed by state/local law)

## 12.7 Product Complaint Reporting

Product complaint reporting and vigilance reporting are applicable and AEs related to any market-released device during the study must be reported. The reporting of product complaints is not part of the study and should be done in addition to the AE reporting requirements. Refer to local regulations for reporting requirements.

**Product Complaint:** Any written, electronic or oral communication that alleges deficiencies related to the identity, quality, durability, reliability, safety, effectiveness or performance of a medical device that has been placed on the market.

- Abuse: Abnormal use (definition acc. #4.1 of Meddev 2.12-1)
- Misuse: Use error (definition acc. #4.20 of Meddev 2.12-1)

It is the responsibility of the investigator to report all product complaint(s) associated with a medical device distributed by Medtronic, regardless whether they are related to intended use, misuse or abuse of the product. Reporting must be done immediately and via the regular channels for market-released products. The reporting of product complaints by the clinical team must be done according to the local Standard Operating Procedures. Medtronic will notify the RAs (e.g. CA) as applicable for the following incidents immediately upon learning of them and is not limited to AEs and DDs only:

- Any malfunction or deterioration in the characteristics and/or performance of a device, as well as any inadequacy in the labeling or instructions for use which led or might have

led to the death or serious deterioration in the state of health of a patient, user, or other person.

- Any technical or medical reason resulting in withdrawal of a device from the market by the manufacturer.
- Any serious deterioration in the state of health, including:
  - Life-threatening illness or injury
  - Permanent impairment of a body function or permanent damage to a body structure
  - A condition necessitating medical or surgical intervention to prevent permanent impairment of a body function or permanent damage to a body structure

## **13. Data Review Committees**

This study will not use a Clinical Events Committee (CEC), Adverse Events Advisory Committee (AEAC), or an independent Data Monitoring Committee (DMC). Instead, regular meetings will be held by sponsor personnel, including the Medical Advisor, to review adverse events and device deficiencies, identify potential trends in safety data during the clinical study, and ensure consistent reporting.

## **14. Statistical Design and Methods**

This section presents statistical considerations for the study design and provides a high-level description of planned analysis and reporting. More details will be given in a separate SAP that will be approved before data freeze or lock for analysis. Any deviation to the pre-specified statistical analyses will be noted in the study report.

### **14.1 General Aspects of Analysis**

Data analysis will be performed by Medtronic-employed statisticians or designees. A validated statistical software package (e.g., SAS version 9.4 or higher) will be used to analyze the study results.

General descriptive statistics for categorical and continuous variables will be used: categorical variables will be summarized as counts and percentages; continuous variables will be presented using mean, standard deviation, median, quartiles and range as applicable.

### **14.1.2 Handling Missing Data**

Missing data are a potential source of bias when analyzing study data. A rigorous study design and execution will help prevent the incidence of missing data from occurring.

The primary analysis of the primary and secondary objectives will include subjects who follow DTM-LE SCS programming and provide data (Per-protocol Analysis Set). Sensitivity analyses will be performed for the primary objective using Completer Analysis Set, as well as Implanted Analysis Set with the Multiple Imputation (MI) methodology for missing data. Details of the imputation method are described in [Section 14.4](#).

### **14.1.3 Multiplicity**

As there is no hypothesis testing for the primary objective, adjustment for multiple endpoints is not required.

### **14.1.4 Investigation Site Pooling**

The investigators of this study will conduct the study according to this protocol and use the same CRFs to collect study data. The site study personnel will be trained prior to the study initiation at each site. Periodic study monitoring by Medtronic will ensure compliance with protocol requirements.

There is no a priori provision to exclude any sites from the analysis. The data from all sites will be pooled for analysis. To reduce the possibility of atypical results from a site overly influencing the combined results, no more than 10 subjects will be enrolled at each site. The per-study site enrollment cap may be increased upon Sponsor approval.

## **14.2 Analysis Execution**

A formal analysis for the DTM-LE SCS study will occur after all subjects complete 3-Month visit. Analysis will include both primary and secondary objectives at 3-Month visit. Additional objectives will be addressed based on available data. A final report will be prepared once all data collection has ended and all subjects have completed the 12-Month visit and have been exited. The analysis for the primary and secondary objectives may be updated for the final report if the analysis is performed before final report. Additional objectives will be addressed based on complete data.

## **14.3 Interim Analysis**

No interim analyses are planned for this study.

## **14.4 Primary Objective**

The primary objective is to characterize changes in overall (back and leg) pain intensity, as measured by visual analog scale (VAS), from Baseline to 3-Month visit in subjects with devices programmed to DTM-LE SCS.

### **14.4.1 Hypothesis**

There is no hypothesis testing for the primary objective. The primary objective is to characterize the overall pain relief from baseline to 3-Month visit in subjects with DTM-LE SCS.

#### **14.4.2 Endpoint definition and derivation**

The measurements of pain intensity using VAS is described in [Section 10.17.1](#). The overall pain intensity as measured by VAS will be collected at both baseline and 3-Month visit. The primary endpoint of change in overall pain VAS is calculated using VAS at the 3-Month visit minus VAS at the baseline visit. A negative change is an improvement.

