### **9.3 Inclusion Criteria**

To be included in this study, a patient must meet the following inclusion criteria:

1. 18 years of age or older
2. Willing and able to provide signed and dated informed consent

3. Capable of comprehending and consenting in English
4. Candidate per labeling for an SCS system (trial and implant) as an aid in the management of chronic, intractable pain of the trunk and/or limbs
5. Has moderate to severe back and leg pain, as determined by the investigator, or designee
6. Baseline VAS is  $\geq 6$  for overall pain
7. Baseline VAS is  $\geq 6$  for back or leg pain
8. ODI score of 21 to 80 out of 100
9. On stable (no change in dose, route, or frequency) pain medications (prescribed and over-the-counter) being used specifically for back and leg pain, as determined by the investigator or designee, for at least 28 days prior to enrolling in the study
10. Willing and able to comply with all study procedures and visits
11. Willing and able to not increase their pain medications (prescribed and over-the-counter) being used specifically for back and leg pain through the 3-month visit
12. Able to differentiate between pain associated with the indication for SCS implant and other types of pain, as determined by the investigator, or designee

Additional inclusion criteria, to be evaluated at device trial/implant:

1. Final lead placements span █ T8 to █ T10 after patient flexion at Device Trial
2. The subject reports  $\geq 50\%$  improvement in overall pain relief at the Device Trial End Visit
3. Final lead placements span █ T8 to █ T10 at Device Implant

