**Table 10-2: Study Visit Target Windows**

Study Visit	Target Window
Baseline	N/A
Device Trial Start	≤ 20 days after Baseline visit
Device Trial End	≤ 7 days after Device Trial Start
Device Implant	≤ 35 days after Device Trial End
Device Activation - Day 0	9-16 days after Device Implant; pending wound healing
1-Month	30 days ± 10 days after Day 0
3-Month	90 days ± 15 days after Day 0
6-Month	180 days ± 30 days after Day 0
12-Month	360 days ± 30 days after Day 0

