## 10.7 Enrollment/Baseline

A subject is considered enrolled when the consent process has been finalized. The date the subject signed the IC and Data Protection Authorization, as required by law, must be documented in the subject's medical records. At the Baseline visit, subjects will be consented prior to any study-related procedures or testing being conducted. Subjects in compliance with inclusion/exclusion criteria will be eligible to participate. A VAS score for overall (back and leg), back, and leg pain will be collected.

Subjects that do not have a VAS  $\geq 6$  cm for overall pain and a VAS  $\geq 6$  cm for either back or leg pain will be exited from the study.

[REDACTED] . Subjects that meet eligibility criteria will proceed with the remaining data collection for the baseline visit and will be scheduled for a device trial. The baseline visit can be a stand-alone visit or can be performed on the same day as the Device Trial Start Visit.

The following information will be collected at the baseline visit:

- Informed Consent
- Inclusion/Exclusion Criteria
- Demographics
- Medical/surgical history
- VAS
- [REDACTED]
- [REDACTED]
- [REDACTED]
- [REDACTED]
- Pain Medications

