### **10.17.1 Visual Analog Scale (VAS)**

Pain will be assessed using a VAS (0-10 cm) with 0 cm meaning “no pain” and 10 cm meaning “worst pain imaginable”. Overall pain is defined as a combination of back and leg pain, but not pain from other body parts. Subjects will be asked to report their average pain intensity (overall, back, and leg) that is related to their SCS device treatment “in the last 24 hours” by marking a line perpendicular to the VAS line at the point that represents their pain intensity. Site personnel will determine the score by measuring the distance (cm) on the 10-cm line between the left, “no pain” anchor and where the subject’s mark meets the line. The total length of the line will be measured (to ensure that it is 10 cm) and the distance from the “no pain” mark to the subject’s mark divided by the total distance of the line will be recorded. The scored VAS ranges from 0 – 10.

The VAS will be collected during the Enrollment/Baseline, 1-, 3-, 6-, and 12-Month visits. The VAS will also be collected at any unscheduled visits, as applicable.

A 6x6 grid of 36 black rectangles of varying widths and heights, arranged in a staggered pattern. The rectangles are set against a white background. The widths of the rectangles range from approximately 1/6 to 5/6 of the grid's width. The heights of the rectangles range from approximately 1/6 to 5/6 of the grid's height. The rectangles are positioned such that they overlap and are not aligned with the grid's rows and columns.

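### The one VAS reading that admits a subject is also the baseline of the primary change, so regression to the mean adds a modest, uncorrected amount to the reported improvement

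*Protocol*

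**What the plan says.** Protocol 9.3 requires a Baseline VAS of at least 6 for overall pain and at least 6 for back or leg pain. Protocol 10.7 applies this at the Baseline visit, after consent: "A VAS score for overall (back and leg), back, and leg pain will be collected", and a subject who does not reach 6 cm overall and 6 "cm for either back or leg pain will be exited from the study".

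Protocol 10.17.1 defines the reading as a single mark for average pain over the previous 24 hours. It gives the schedule as "The VAS will be collected during the Enrollment/Baseline, 1-, 3-, 6-, and 12-Month visits", and adds "The VAS will also be collected at any unscheduled visits, as applicable". Table 10-1 agrees: no VAS at Device Trial Start, Mid-Trial, Trial End, Implant or Activation. Trial success (10.8.3) is a subject-reported percent improvement, not a VAS.

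The primary endpoint (Protocol 14.4.2, repeated in SAP 7.9.1.2) is "calculated using VAS at the 3-Month visit minus VAS at the baseline visit". It is summarised as a mean with a 95% CI (14.4.3), in one open-label arm, without a hypothesis test (14.4.1). The two sensitivity analyses (14.4.4, SAP 7.9.1.4) change the analysis set and the handling of missing data, but not the baseline.

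Protocol 14.9 names selection of subjects as a possible source of bias. The measures it lists concern missing data and the per-site cap.

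**The concern.** A 24-hour pain recall varies from day to day. A lower limit applied to one such reading keeps subjects who were having a worse day than usual and removes those having a better one. The mean of the retained readings is then higher than those subjects' usual pain, and a later reading would be lower on average with no treatment at all. When the qualifying reading is also the one subtracted, that fall is counted as improvement.

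A concurrent control arm would show the same fall and let it cancel, but there is none here. The CI describes sampling variation around the shifted mean and does not include the shift. The same baseline also enters the percent change (14.4.3), the 1-, 6- and 12-Month changes (SAP 7.9.3.1) and the test for less than a 50% decrease at which a subject may be re-programmed (10.12.1 to 10.12.3). At stake is how the estimate is read: 14.4.1 describes the change as pain relief with DTM-LE, and Section 6 describes the study as evaluating efficacy.

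**Working it through.** **1. The plan's own precision.** Half-width = t(0.975, n − 1) × SD / √n. With n = 30 and SD 2.6 (Protocol 14.8): 2.045 × 2.6 / √30 = 0.971. The stated 0.97 reproduces. Enrollment: 30 / 0.90 / 0.60 = 55.6, so 56 reproduces.

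**2. Formula for the shift.** Take two readings on the same subject with equal mean and SD, correlation ρ, bivariate normal, and no treatment effect. Selecting on the first reading being at least 6 gives

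expected fall = (1 − ρ) × SD × φ(z) / (1 − Φ(z)), with z = (6 − mean) / SD.

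Φ(z) is the share failing the cut, so the formula can be driven by that share instead of by an assumed mean.

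**3. What limits the share failing.** Consent precedes the VAS, so a subject exited for VAS counts as enrolled and as a screen failure (9.2, 10.7). Protocol 14.8 assumes 40% total loss from enrollment to implant. That must also cover failed device trials, unsuitable lead placement and other reasons, so VAS failures should be well under 40%.

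**4. Results.** The documents give no SD of a single reading in candidates, no ρ and no failure share. Assumptions: SD 1.5 to 2, ρ 0.6 to 0.8, failure share as shown.

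| Share failing | z | φ(z) / (1 − Φ(z)) | Smallest: 0.2 × 1.5 × ratio | Largest: 0.4 × 2 × ratio |
|---|---|---|---|---|
| 10% | −1.28 | 0.1755 / 0.90 = 0.195 | 0.06 cm | 0.16 cm |
| 20% | −0.84 | 0.2800 / 0.80 = 0.350 | 0.11 cm | 0.28 cm |
| 40% (the whole allowance) | −0.25 | 0.3863 / 0.60 = 0.644 | 0.19 cm | 0.52 cm |

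Simulating the same cases with readings clipped to 0 to 10 changed no value by more than 0.003 cm, so the scale ceiling does not drive the result. Only the overall-pain cut is modelled; the back-or-leg cut and the 50% trial criterion are not.

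**5. Scale.** 0.28 / 0.97 = 29% of the planned half-width, and 0.52 / 0.97 = 53%. A 50% reduction from a baseline of 6 is 3 cm, and 0.28 / 3 = 9% of that.

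**6. Timing.** The Table 10-2 upper limits from Baseline to activation are 20 days, 7 days, "≤ 35 days after Device Trial End" and 16 days: 20 + 7 + 35 + 16 = 78. The opening text of 10.8 allows 14 days instead of 20 for the first step, giving 14 + 7 + 35 + 16 = 72. Up to 7 of these days are trial stimulation. The interval before any stimulation is at most 20 days, and is zero when Baseline and Device Trial Start share a day, which 10.7 permits.

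**The case against.** The strongest reply is that the objective is to characterise change, with no test and no claim against a comparator, and that a single-arm before-after change is an openly declared design. It is also fair that the plausible shift is small beside the size of change the study looks for. Both points stand. They limit the weight of the concern but do not remove it, because an estimation study rests on its estimate and this shift has a known direction.

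Several stronger readings are tempting, and the documents do not support them:

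- *The shift could exceed the CI half-width.* A candidate mean of 5, SD 2.6 and ρ 0.5 would give 1.38 cm, and a mean of 6, SD 2 and ρ 0.6 would give 0.64 cm. But a mean of 6 or lower has at least half of enrolled subjects failing the cut, more than the 40% total loss the plan assumes. That 40% is itself a planning figure, so this argues against such values without excluding them.
- *The shift cannot be estimated from the data collected.* The Baseline VAS is taken before the exit decision (10.7), and data up to exit are used (10.21). The mean and SD before the cut are therefore largely estimable among enrolled subjects. The correlation can be approximated from the follow-up readings, imperfectly because stimulation is on.
- *All 78 days are unstimulated, or 78 is a ceiling.* Neither is so. Trial stimulation falls inside the interval, the figures are target windows, and activation waits for wound healing.
- *No pain at all is measured before the 1-Month visit.* Only the VAS schedule is readable. An unscheduled visit may yield a VAS, and parts of the assessment section are redacted.
- *The change from Baseline to Activation would measure regression to the mean.* By then subjects have had trial stimulation, been selected for at least 50% relief, undergone surgery and possibly changed medication.

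**Conclusion.** The concern holds as a bias of known direction and modest size. One 24-hour reading both selects subjects and anchors the primary change. No second VAS is scheduled before stimulation, nothing in the design offsets the effect, and 14.9 does not mention it. Under the stated assumptions, which are not in the documents, the expected spurious improvement is about 0.06 to 0.28 cm. The upper limit is about 0.5 cm if every planned pre-implant loss were a VAS failure. This is below the 0.97 cm half-width throughout, but the CI does not account for it.

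A reader might infer that the primary analysis is invalid or that an error rate is inflated. Neither follows: nothing is tested, and the endpoint can stand if the shift is estimated and disclosed. The point is worth acting on mainly because the remedy is cheap.

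**What to change.** Keep the Baseline VAS for eligibility and keep the primary endpoint as defined.

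1. **Table 10-1, 10.8.1 and 10.17.1:** add the overall, back and leg VAS at Device Trial Start, before lead placement, when that visit is on a different day from Baseline.
2. **SAP 7.9.1:** add a supportive analysis of change to 3 months from the Device Trial Start reading, in the subjects who have it. Report the change from Baseline to Device Trial Start as the estimate of regression to the mean plus short-term natural course.
3. **Same-day subjects:** report a model-based correction using the Baseline VAS of all enrolled subjects, including those exited for a VAS below 6. State the correlation used and show a range. This part needs no new visit data.
4. **Optional:** a VAS at Activation before the stimulator is turned ON. Show it separately and describe it as mixing regression to the mean, trial carry-over, responder selection, surgery and medication changes. Do not pool it with the Device Trial Start reading.
5. **Protocol 14.9 and the study report:** state the limitation. If it is too late to add readings, items 3 and 5 can still be done.
6. **Reconcile** the 14-day limit in the opening text of 10.8 with the 20 days in 10.8.1 and Table 10-2, since this sets how far apart the two readings can be.

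The cost is one short form at a visit already held, one change to a row of Table 10-1, and a small addition to the SAP. The supportive estimate may be slightly less favourable than the primary one.
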